### **Restricted Mean Survival Time (RMST)**

The hazard ratio estimate from the Cox's PH model is routinely used to empirically quantify the between-arm difference under the assumption that the ratio of the two hazard functions is constant over time. When this assumption is plausible, such a ratio estimate may capture the relative difference between two survival curves. However, the clinical meaning of such a ratio estimate is difficult, if not impossible, to interpret when the underlying PH assumption is violated (i.e., the hazard ratio is not constant over time).

The RMST is a robust and clinically interpretable summary measure of the survival time distribution and is equivalent to the area under the Kaplan-Meier curve from 'start date' through a specific cut-off point. Unlike median survival time, it is estimable even under heavy censoring. There is a considerable body of methodological research (e.g., Royston and Parmar, 2011, Uno, Wei, et al., 2014; Zhang, 2013) about the use of RMST to estimate treatment effects as an alternative to the hazard ratio approach.

The RMST methodology is applicable independently of the PH assumption and can be used, at a minimum, as a sensitivity analysis to explore the robustness of the primary analysis results. However, when large departures from the PH assumption are observed, the log-rank test is underpowered to detect differences between the survival distributions for the treatment arms, and a test of the difference between the RMST for the experimental arm and the control arm may be more appropriate to determine superiority of the experimental arm compared to the control arm with respect to the time-to-event endpoint.

In particular, as it pertains to the **cut-off point ( $\tau$ )** to evaluate the RMST, it is noted that the cut-off point should not exceed the minimum of the largest observed time for both treatment arms so that the RMST of all treatment arms being evaluated can be adequately estimated and comparison between treatments is feasible;  $\tau$  should be clinically meaningful and closer to the end of the study follow-up so that the majority of survival outcomes will be covered by the time interval. The RMST up to time  $\tau$  can then be interpreted as the expected survival time restricted to the common follow-up time  $\tau$  among all participants. To avoid arbitrary selection of the common cut-off  $\tau$  for both treatment arms,  $\tau$  is pre-specified as:

$\tau$  = minimum of (largest observed EFS time for the experimental arm, largest observed EFS time for the control arm).

The treatment effect between the experimental arm and the control arm will be assessed based on the difference in RMST. The associated 95% CI for the difference in means and 1-sided p-value will be generated.

### **BICR vs Investigator Assessment**

A summary of BICR evaluation of investigator-assessed EFS will be provided:

- Number and percentage of participants with a non-death EFS event as assessed by the investigator
- Number and percentage of participants with an investigator-assessed non-death EFS event confirmed by BICR.

### **Exploratory analyses to investigate the impact of potential prognostic or effect modifying (predictive) factors**

See subgroups as defined in [Section 6.4](#).

Multivariable Cox's regression analysis will be carried out to assess and adjust the treatment effect for relevant baseline factors of potential prognostic impact. A stepwise selection procedure will serve to identify explanatory variables of potential prognostic values additional to the randomization strata which will be included in all models during the selection procedure. The Cox's Proportional Hazard model is defined as:

$$h(t) = h(0;t) e^{Xb}$$

where  $h(0;t)$  defines the baseline hazard function and  $X$  defines the vector of explanatory variables and  $b$  the unknown vector of regression parameters.

In the stepwise selection procedure, variables are entered into and removed from the model in such a way that each forward selection step can be followed by one or more backward elimination steps. The stepwise selection process terminates if no further variable can be added to the model or if the variable just entered into the model is the only variable removed in the subsequent backward elimination. The level of significance for an explanatory variable to enter the model is set to 0.15 (p-value of Score test) and the significance level for removing it is set to 0.40 (p-value of Wald test). This analysis will be performed using the stepwise selection method in SAS (Proc PHREG). Once this procedure stops, the factor "treatment arm" will be added to the last selected model in order to evaluate the effect of treatment on EFS time when adjusted for the selected explanatory variables. The hazard ratios of all selected explanatory variables and of treatment effects will be reported including 2-sided 95% CIs. No interactions will be considered. Post-baseline factors will not be considered for the model.

#### **6.2.2.4. Sensitivity analysis for OS (Cohort A only)**

The following sensitivity analyses will be performed to explore the robustness of the primary analysis results for OS. These analyses are regarded as purely exploratory. The sensitivity analyses will repeat the primary analysis (p-value, HR and 95% CIs) described in [Section 6.2.2.2](#) with the modifications below:

- PP analysis set;
- Unstratified;
- If >10% of deaths are due to COVID-19, an analysis will be performed for non-COVID-19 related deaths by treating COVID-19 related deaths as a competing risk event.

#### **Methods for evaluating the validity of model assumptions**

The same methodology described in [Section 6.2.2.3](#) for EFS will be used for OS.

#### **Exploratory analyses to investigate the impact of potential prognostic or effect modifying (predictive) factors**

The same methodology described in [Section 6.2.2.3](#) for EFS will be used for OS.

#### **6.2.2.5. Complete response (participants with CIS at randomization) (Cohort A only)**

Complete Response (CR) is defined as histologic disappearance of malignancy on bladder biopsy with negative cytology and cystoscopy or negative cytology and positive cystoscopy with biopsy-proven low-grade Ta lesion or nonmalignant tissue for participants with CIS at randomization according to the CRF.

CR rate for participants with CIS at randomization will be calculated with the 2-sided 95% CI using the Clopper-Pearson method (exact CI for a binomial proportion as computed by default by the FREQ procedure using the EXACT option) for each treatment arm.

The difference in CR rates between each experimental arm (Arm A and Arm B) and the control arm (Arm C) will be tested with a 2-sided p-value using a stratified analysis stratified

by the randomization stratum of geographic region. The Mantel-Haenszel (MH) test and MH confidence limits will be obtained through PROC FREQ using the option of COMMONRISKDIFF(CL=MH Test=MH), which tests the null hypothesis that the common risk difference is 0.

### **BICR biopsy evaluation of investigator-assessed CR**

For the participants with CIS at randomization by the investigator, the following will be presented:

- Number of participants achieved CR as assessed by the investigator
  - Number of participants achieved CR as assessed by the investigator which was confirmed by investigator biopsy assessment.
    - BICR agreed (investigator-assessed CR confirmed by BICR biopsy assessment).
    - BICR disagreed (investigator-assessed CR not confirmed by BICR biopsy assessment).
    - No BICR biopsy assessment (biopsy not available/evaluable for BICR assessment).

If there are >5% of participants who discontinued treatment due to COVID-19 prior to achieving CR, a sensitivity analysis based on cumulative incidence curve will be performed for CR to estimate the CR rate by treating COVID-19 related discontinuation as censoring.

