8.1.1.1. Cystoscopy

Cystoscopy should be performed and assessed using the same method and equipment by the same study staff (whenever possible), for the duration of the study, in order to reduce subjectivity across multiple assessments. White light, blue light or narrow-band imaging are allowed in this study and blue light is preferred. Number, size and location of the tumors should be documented.

Disease status will be assessed through cystoscopy conducted at screening, every 12 weeks for 2 years following randomization, and every 24 weeks during the rest of follow-up, and as clinically indicated. Timing of disease assessment is to be fixed according to the calendar (± 7 days) starting with randomization for Cohort A and initiation of study intervention for Cohorts B1 and B2, and should not be adjusted for study intervention dose modifications. Please refer to the Schedule of Activities for disease assessment time points for each Cohort.

Cystoscopy with biopsy is required at the time of recurrence of high-grade disease, disease progression, persistence of CIS (applicable only to participants with CIS at randomization), or complete response (applicable only to participants with CIS at randomization) as described in Section 10.9.

In Cohort A, biopsy for confirmation of complete response for participants with CIS should be performed at the 24 week disease assessment, unless collection at the 12 week disease assessment is routinely performed at the given institution. Please consider that if the bladder biopsy collection at the Week 12 disease assessment fails to confirm CR, the biopsy collection must be repeated at the Week 24 disease assessment. If it is not possible to perform the bladder biopsy collection by the Week 24 disease assessment, biopsies should be collected as soon as possible at the next scheduled disease assessment.

Timing of disease assessment is to be fixed according to the calendar (± 7 days), starting with randomization for Cohort A, and initiation of study intervention for Cohorts B1 and B2, and should not be adjusted for study treatment dose modifications.

For cystoscopy without biopsy, either flexible or rigid cystoscopy may be conducted as per the Investigator's clinical judgement or institutional guidance/preference. Further specifications for the procedure are provided in the Study Manual.

For cystoscopy with biopsy, a full thickness tissue specimen is required to be obtained and Sponsor recommends a rigid cystoscopy.

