- Cystoscopy with collection of random biopsies from bladder (dome, trigone, right and left lateral wall, and anterior and posterior wall) and prostatic urethra in male participants OR collection of suspicious lesions, if present;
- Cytology;
- Imaging

No Evidence of Disease only applies to participants without CIS at baseline (Cohort A and Cohort B2) and is defined as disease that was completely resected prior to randomization (Cohort A)/initiation of study intervention (Cohort B2) and does not meet the criteria of progression of disease, recurrence of high-grade disease, or recurrence of low-grade disease while on study. The date of imaging, biopsy, cystoscopy, or cytology (whichever result of the available assessments is earliest) that supports no evidence of disease will be used as the date of no evidence of disease.

Complete Response, in participants with CIS at baseline, is defined as histologic disappearance of malignancy on bladder biopsy with negative cytology and cystoscopy or negative cytology and positive cystoscopy with biopsy-proven low-grade Ta lesion or non-malignant tissue. The date of biopsy, cystoscopy, or cytology (whichever is earliest) will be used as the date of Complete Response. See section 8.1.1.1 for guidance regarding timing of these biopsies.

Persistence of CIS, in participants with CIS at baseline in Cohort A, is defined as persistence of CIS after induction or re-induction (if re-induction is administered). For participants in Cohort B1, persistence of CIS is defined as persistence of CIS at the 12 week or 24 week disease assessment. This will require a cystoscopy or cytology positive result with biopsy positive for CIS. The date of positive biopsy, cystoscopy, or cytology (whichever positive result is earliest) will be used as the date of persistence of CIS.

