### 2.1. Modifications to the Analysis Plan Described in the Protocol

Changes	Protocol	SAP
Cohort A: Complete response as assessed by BICR	Specified	Removed
Cohort A: Duration of CR as assessed by BICR	Specified	Removed

The removal of the analysis of complete response (CR) and duration of CR (DoCR) by BICR described in the protocol is based on the infeasibility of these analyses without large amount of data imputations based on investigator assessment. As per protocol, on-study biopsy is not required at each disease assessment visit, therefore central pathology assessment of CR could not be performed at each visit, and independent oncology review of CR is not feasible.

In addition, to adhere to the requirements from the FDA with reference to independent evaluation of EFS events and CR, the following summaries were added:

- BICR oncology evaluation of investigator-assessed EFS events (Section 6.2.2.3).
- BICR biopsy evaluation of investigator-assessed CR (Section 6.2.2.5).

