### **3.2.2. Efficacy endpoints**

#### Cohort A

- Key Secondary: EFS for Arm B vs Arm C as assessed by the investigator

EFS is defined as time from randomization to the earliest of recurrence of high-grade disease, progression of disease, persistence of CIS, or death due to any cause.

- Key Secondary: OS  
OS is defined as the time from the date of randomization to the date of death due to any cause.
- EFS as assessed by the BICR  
EFS is defined as time from randomization to the earliest of recurrence of high-grade disease, progression of disease, persistence of CIS, or death due to any cause.
- CR as assessed by the investigator (in participants with CIS at randomization)  
CR is defined as histologic disappearance of malignancy on bladder biopsy with negative cytology and cystoscopy or negative cytology and positive cystoscopy with biopsy-proven low-grade Ta lesion or non-malignant tissue
- DoCR for participants with CR as assessed by the investigator (in participants with CIS at randomization)

DoCR is defined as the time from the first documentation of CR to the date of an EFS event for participants with CR.

- Time to recurrence of low-grade disease as assessed by the investigator

Time to recurrence of low-grade disease is defined as the time from randomization to the date of first documentation of recurrence of low-grade disease.

- Time to cystectomy

Time to cystectomy is defined as time from randomization to cystectomy.

- DSS as assessed by the investigator

DSS is defined as the time from randomization to death resulting from bladder cancer, as assessed by the investigator.

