### 6.2.2. Efficacy endpoints

The following analyses will be based on the FAS by treatment arm for Cohort A and for Cohorts B1 and B2, unless otherwise specified. Summaries will only be provided for Cohort A. For Cohorts B1 and B2, listings will be provided for efficacy endpoints as indicated.

For Cohort A, disease endpoints (CR, DoCR, time to recurrence of low-grade disease, and DSS) will be analyzed based on investigator assessment. EFS by BICR assessment will be analyzed as a secondary endpoint using the same methodology that is described in [Section 6.1.1.1](#) now referring to BICR assessment instead of investigator assessment.

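### SAP 6.2.2.5 defines complete response by bladder histology, but analyses investigator-assessed CR and its duration without restricting them to biopsy-confirmed cases

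*SAP*

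**What the plan says.** **Definition.** SAP 6.2.2.5 states: "Complete Response (CR) is defined as histologic disappearance of malignancy on bladder biopsy with negative cytology and cystoscopy". The alternative route, with a positive cystoscopy and negative cytology, also needs a biopsy, showing low-grade Ta or non-malignant tissue. SAP 5.2.12 and protocol 10.9 give the same two routes.

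**Analysis.** SAP 6.2.2 says that in Cohort A "disease endpoints (CR, DoCR, time to recurrence of low-grade disease, and DSS) will be analyzed based on investigator assessment". SAP 6.2.2.5 continues: "CR rate for participants with CIS at randomization will be calculated with the 2-sided 95% CI using the Clopper-Pearson method", followed by a Mantel-Haenszel test of the risk difference stratified by region. No sentence limits the responders to those with a biopsy. The only CR sensitivity analysis concerns COVID-19 discontinuations. DoCR (SAP 6.2.2.6) starts at the first documented CR, and SAP 5.2.12 dates CR at the earliest of biopsy, cystoscopy or cytology.

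**Agreement table.** Also in 6.2.2.5, a descriptive table counts all investigator-assessed CRs and, nested beneath, "Number of participants achieved CR as assessed by the investigator which was confirmed by investigator biopsy assessment". Beneath that come three lines: the central biopsy review agreed, disagreed, or had no biopsy to assess.

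**Biopsy timing.** Protocol 8.1.1.1 requires cystoscopy with biopsy at complete response. It places the confirming biopsy at Week 24, "unless collection at the 12 week disease assessment is routinely performed at the given institution", asks for a repeat at Week 24 if the Week 12 biopsy does not confirm, and lets a missed biopsy move to the next scheduled assessment. SAP 2.1 drops CR by central review, giving as a reason that "on-study biopsy is not required at each disease assessment visit".

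**Missing data.** Protocol 9.4.1.1 counts participants with inadequate disease-assessment data as non-responders for CR. SAP 6.2.2.5 does not repeat this.

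**The concern.** The endpoint and its count are specified differently. By definition a CR cannot exist without histology, but the numerator is whatever the investigator recorded as CR, and the SAP's own table has a separate, lower tier for those that a biopsy confirmed. Investigator CRs outside that tier have no line in the table and no handling rule.

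CR and DoCR are named secondary endpoints. If unconfirmed CRs enter, the published rate is not the rate of the endpoint as written, and it depends partly on whether a site routinely takes a Week 12 biopsy. DoCR can also pick up short durations from participants whose first biopsy then shows CIS.

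**Working it through.** **Is there a planned figure to reproduce?** Not for this endpoint: the documents give no Cohort A CR rate, CR power or unconfirmed share. As a check of the interval method only, exact Clopper-Pearson limits for SAP Table 8 (Cohort B1, n = 100) were recomputed. All nine intervals match to two decimals; 40/100, for example, gives 30.33% to 50.28%.

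**Can a CR be recorded without a biopsy?** Take a participant with CIS who has clean cystoscopy and cytology at Week 12, at a site that does not routinely biopsy then.

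- Persistence of CIS needs a CIS-positive biopsy (SAP 5.2.12), so it cannot be recorded.
- No evidence of disease applies only to participants without CIS (SAP 5.2.12).
- What remains is CR, or not evaluable (SAP 5.2.11).

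The categories therefore leave room for a CR entry ahead of histology, although the definition does not permit one.

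**Effect on the rate.** Let R be the reported all-investigator rate and u the share of those CRs never confirmed by biopsy.

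- Confirmed rate = R × (1 − u)
- Excess of the reported rate = R × u

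Both R and u below are assumptions, shown as a range. At u = 0 the excess is 0.

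| R | u = 10% | u = 20% | u = 30% |
|---|---|---|---|
| 60% | 6.0 points | 12.0 points | 18.0 points |
| 80% | 8.0 points | 16.0 points | 24.0 points |
| 90% | 9.0 points | 18.0 points | 27.0 points |

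In participants, assume the planned minimum of 250 with CIS split equally: 250/3 ≈ 83 per arm. With R near 80%, rounding to whole participants:

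- u = 0: 66/83 = 79.5% (exact 95% CI 69.2% to 87.6%)
- u = 10%: 60/83 = 72.3% (61.4% to 81.6%)
- u = 20%: 53/83 = 63.9% (52.6% to 74.1%)
- u = 30%: 46/83 = 55.4% (44.1% to 66.3%)

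**Effect on the arm difference.** Assume reported rates of 85% (experimental) and 75% (control), a difference of 10.0 points. The confirmed-only difference is 0.85 × (1 − u_E) − 0.75 × (1 − u_C):

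- u = 20% in both arms: 68.0% − 60.0% = 8.0 points
- u_E = 20%, u_C = 10%: 68.0% − 67.5% = 0.5 points
- u_E = 10%, u_C = 20%: 76.5% − 60.0% = 16.5 points

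The difference can shrink or grow, depending on u in each arm.

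**Effect on DoCR.** If the Week 12 participant above were entered as CR and the Week 24 biopsy showed CIS, the SAP formula would give (84 + 1)/30.4375 = 2.8 months of response. Under the definition that participant is a non-responder and does not enter DoCR.

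**The case against.** The strongest reply is that the governing text already demands histology. SAP 5.2.12 says disease is assessed by its rules, both CR routes there need a biopsy, and protocol 8.1.1.1 requires a biopsy at CR. On that reading every investigator CR has histology, the nested row only sets up the comparison with central review, and the protocol's non-responder rule catches any gaps. CR is also outside the tested hierarchy, and since both tiers are to be shown by arm, a reader could work out the confirmed rate.

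Much of this stands. A reader might infer that the SAP admits to CRs without a biopsy. It does not: the nested row implies the possibility, and SAP 2.1 says only that biopsies are not taken at every visit. A reader might also infer a bias favouring the experimental arms because the trial is open-label. The biopsy schedule is the same in all arms, and the arithmetic shows no fixed direction. A deferred biopsy that turns out negative confirms the CR and inflates nothing.

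It does not close the gap. If every counted CR met the definition, the two tiers would be equal and the second redundant. Nor can that tier mean only that material was unavailable to central review, because this has its own line below. The non-responder rule is missing from SAP 6.2.2.5, and neither document says whether a missing confirmatory biopsy is inadequate data. The descriptive counts leave the interval, the test and DoCR on the unrestricted set.

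**Conclusion.** The point holds in a conditional form. The analysis of CR and DoCR carries no biopsy restriction although the endpoint is histologic, and the plan makes CRs recorded without a biopsy plausible. If any are counted, the reported rate is too high for the defined endpoint by R × u: from 6 to 27 points over the assumed grid (R 60% to 90%, u 10% to 30%), and nothing if u = 0. The documents supply neither R nor u, and the 83 per arm is the planned minimum divided by three, not an enrolled count.

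The stronger statement that the CR rate is overstated is not supported, since u may be zero. The formula also applies to the reported rate, not to a true rate: 15% of a true 90% is 13.5 points, and adding it would give an impossible 103.5%.

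The four alpha-controlled hypotheses concern EFS and OS, so the primary and key secondary conclusions are unaffected.

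**What to change.** In SAP 6.2.2.5 and 6.2.2.6, run the CR rate, its interval, the Mantel-Haenszel difference and DoCR by arm on investigator CRs whose biopsy meets the histologic definition in SAP 5.2.12. Accept a biopsy at that assessment or the deferred confirmatory biopsy that protocol 8.1.1.1 allows. Count CRs never confirmed by biopsy as non-responders, and state that this applies the inadequate-data rule of protocol 9.4.1.1. Report the all-investigator rate alongside, and add a line to the agreement table for unconfirmed CRs by arm. At minimum, prespecify the confirmed-only analysis as a sensitivity analysis.

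The cost is a sentence or two in the SAP and a flag that the planned agreement table already needs. The biopsy schedule does not change. The downside is that the stated CR rate may be lower and DoCR may rest on fewer participants.
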